11.2.1 Serious Adverse Experience Reporting

Study sites will document all SAEs that occur (whether or not related to study treatment) per UCSF CHR Guidelines. The collection period for all SAEs will begin after informed consent is obtained and end after procedures for the final study visit have been completed.

In accordance with the standard operating procedures and policies of the local Institutional Review Board (IRB)/Independent Ethics Committee (IEC), the site investigator will report SAEs to the IRB/IEC.

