	sponges to enhance cooling of the renal parenchyma during the	
	anhepatic phase of the operation.	
CONTROL	Normothermia (36.5-37.5 °C) during liver transplantation	
TREATMENT AND	romotiona (50.5 57.5 °C) during irver dunsplanation	
METHOD OF	Normothermia will be maintained using an ECD as well as standard	
ADMINISTRATION	measures after the induction of general anesthesia and throughout the	
	liver transplant operation.	
	Subjects will be on study for up to one year.	
DURATION OF	Screening: less than 1 day	
SUBJECT PARTICIPATION	Treatment: less than 1 day (during liver transplantation)	
	Follow-up: 1 year	
AND DURATION OF	The total duration of the study is expected to be 36 months. 24	
STUDY	months for subject recruitment and 12 for final subject follow-up.	
CONCOMMITANT	Allowed: N/A	
MEDICATIONS	Allowed. N/A	
MEDICATIONS	Prohibited: N/A	
FEELCACY		
EFFICACY EVALUATIONS		
PRIMARY ENDPOINT	Incidence of acute kidney injury within 72 hours after liver	
TRIMARI ENDI OINT	transplantation	
SECONDARY	 Distribution of the stages of acute kidney injury within 72 hours 	
ENDPOINTS	after liver transplantation	
	 Duration of intensive care unit stay 	
	 Duration of hospital stay 	
	 One-year survival rate 	
	 Need for renal replacement therapy within 7-days, at 30-days, and 	
	at 1 year after transplant	
	 Persistent renal dysfunction at 90-days and 1-year after transplant 	
	 Change in serum NGAL levels from baseline to 2 hours after 	
	reperfusion of the portal vein	
	 Change in urine NGAL levels from baseline to 2 hours after 	
	reperfusion of the portal vein	
OTHER	Percentage of intraoperative time within target temperature range	
EVALUATIONS	i i oreentage of intraoperative time within target temperature range	
LIALUAIIUNS	 	

SAFETY EVALUATIONS	 Time to reach normothermia upon initiation of re-warming (mild hypothermia arm) Number of units of blood products transfused (packed red blood cells, fresh frozen plasma, platelets, and cryoprecipitate) Incidence of surgical site infections within 2 weeks of LTx Intraoperative vasopressor doses
PLANNED INTERIM ANALYSES	When 50% of patients have completed the study, an interim analysis for efficacy will be conducted by an independent data safety monitoring board (DSMB).

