10 EVALUATIONS BY VISIT

10.1 Visit 1 (Day 1, before and during LTx)

- 1. Review the study with the subject (subject's legal representative) and obtain written informed consent and HIPAA authorization and assent, if appropriate.
- 2. Assign the subject a unique screening number.
- 3. Record demographics data.
- 4. Record medical history, including a history of acute kidney injury, ascites, or hepatic encephalopathy, including diagnosis date, and prior treatments (dialysis, continuous renal replacement therapy (CRRT), large volume paracentesis).
- 5. Record concomitant medications.

- 6. Perform a complete physical examination.
- 7. Perform and record vital signs.
- 8. Perform and record oximetry.
- 9. Perform and record results of blood pressure testing.
- 10. Randomize subject (see Section 8.1).
- 11. Place ECD after induction of general anesthesia.
- 12. Implement intraoperative temperature protocol according to randomization (see Section 8.3).
- 13. Collect blood for ABGs (see Section 9.2) and NGAL determination (Section 9.3.1).
- 14. Collect urine for NGAL determination (see Section 9.3.2).
- 15. Remove ECD at the end of surgery.
- 10.2 Visit 2 (Follow-up prior to hospital discharge, window of 2 ± 1 weeks after LTx)
- 1. Record any Adverse Experiences.
- 2. Record changes to concomitant medications.
- 3. Perform complete physical examination.
- 4. Perform and record vital signs.
- 5. Perform and record oximetry.
- 6. If surrogate consent was obtained for the subject, and subject has now regained capacity, re-consent the patient for use of study data.

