11 ADVERSE EXPERIENCE REPORTING AND DOCUMENTATION

11.1 Adverse Events

An adverse event (AE) is any untoward medical occurrence in a clinical investigation of a patient administered a treatment that does not necessarily have a causal relationship with the treatment. An AE is therefore any unfavorable and unintended sign (including an abnormal laboratory finding), symptom or disease temporally associated with the administration of an investigational treatment, whether or not related to that investigational treatment.

The Investigator will probe, via discussion with the subject, for the occurrence of AEs during each subject visit and record the information in the site's source documents. Adverse events will be recorded in the patient CRF. Adverse events will be described by duration (start and stop dates and times), severity, outcome, treatment and relation to study protocol, or if unrelated, the cause.

AE Severity

The National Cancer Institute's Common Terminology Criteria for Adverse Events (CTCAE) Version 3.0 should be used to assess and grade AE severity, including laboratory abnormalities judged to be clinically significant. The modified criteria can be found in the study manual. If the experience is not covered in the modified criteria, the

guidelines shown in Table 1 below should be used to grade severity. It should be pointed out that the term "severe" is a measure of intensity and that a severe AE is not necessarily serious.

Severity (Toxicity Grade)	Description
Mild (1)	Transient or mild discomfort; no limitation in activity; no medical
	intervention or therapy required. The subject may be aware of the sign
	or symptom but tolerates it reasonably well.
Moderate (2)	Mild to moderate limitation in activity, no or minimal medical
	intervention/therapy required.
Severe (3)	Marked limitation in activity, medical intervention/therapy required,
	hospitalizations possible.
Life-threatening (4)	The subject is at risk of death due to the adverse experience as it
	occurred. This does not refer to an experience that hypothetically
	might have caused death if it were more severe.

Table 1. AE Severity Grading

AE Relationship to Study Treatment

The relationship of an AE to the study treatment should be assessed using the following the guidelines in Table 2.

Relationship to Drug	Comment	

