APPENDIX 1. SCHEDULE OF STUDY VISITS

	VISIT 1 (Day 1, before and during liver transplant)	VISIT 2 (Day 2, prior to hospital discharge, approximately 2 weeks after LTx) ^A
Informed Consent	X	X ^B
Medical History	X	
Complete Physical Exam	X	X
Height	X	
Weight	X	
Vital Signs	X	X
Oximetry	X	X
Randomization	X	
Administration of Study Treatment	X	
Blood and Urine collection	X	
Initiate Subject Diary	X	
Subject Diary Review		X
Concomitant Medication Review	X	X
Adverse Experiences		X

^A ±1 week

^B Consent from subject will be obtained for use of study data if the patient lacked capacity and Surrogate Consent was obtained during Visit 1.

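### SAE collection most naturally closes at a pre-discharge visit, so post-operative safety follow-up varies with length of stay; the surgical site infection rule has the same dependence

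*Combined protocol and SAP*

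**What the plan says.** **End of collection.** Under Section 11.2.1, SAE collection starts once consent is given and will "end after procedures for the final study visit have been completed". That final visit is not named. Section 10 and Appendix 1 list two visits only. Section 10.2 describes the second as "Follow-up prior to hospital discharge, window of 2 ± 1 weeks after LTx". After it, Section 4.1 provides remote follow-up through the electronic record for a year, which it does not call a visit. The synopsis adds: "Subjects will be on study for up to one year".

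**AE recording.** Section 9.1.6 has AEs captured over the whole study, with start and stop times on the CRF. Section 11.1 states: "The Investigator will probe, via discussion with the subject, for the occurrence of AEs during each subject visit". In the visit lists, however, "Record any Adverse Experiences" is an item of Visit 2 only; none of the 15 Visit 1 steps is an AE step. Appendix 1 likewise marks adverse experiences under Visit 2 alone, and heads that column "Day 2, prior to hospital discharge, approximately 2 weeks after LTx".

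**Surgical site infection.** Section 5.3E counts infections to discharge or to two weeks, whichever is earlier. The synopsis gives two weeks without reference to discharge.

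**Length of stay.** Duration of hospital stay is secondary efficacy endpoint C in Section 5.2.

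**The concern.** When observation ends at a visit that must precede discharge, the time at risk becomes partly a result of the patient's course after randomization. An arm with longer stays is watched for longer and can show more post-operative events with no true difference in risk; an arm with shorter stays can look safer than it is.

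The protocol gives a reason to expect that stay could differ by arm. Section 2.1 says that AKI severity goes with longer hospital stay, and the trial aims to reduce AKI. Surgical site infection is also one of the hypothermia risks that Section 2.1 names, so a discharge-dependent count falls on an outcome of direct interest. Section 15.4 tabulates AEs by treatment group as numbers of patients and rates, with no adjustment for time observed.

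**Working it through.** **1. The Visit 2 window.** 2 ± 1 weeks = 14 ± 7 days = day 7 to day 21. The ratio of longest to shortest is 21 / 7 = 3. Because the visit must come before discharge, the latest possible closing date is the smaller of the discharge day and day 21.
- Discharge before day 7: no date is both pre-discharge and in window.
- Discharge between day 7 and day 21: length of stay sets the upper limit.
- Still in hospital after day 21: an in-window visit closes collection while the patient is an inpatient.

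**2. The infection window.** Section 5.3E gives the smaller of discharge day and day 14; the synopsis gives day 14. They agree only for patients who stay at least two weeks.

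**3. What a shorter window does to one rate (illustration).** The documents give no post-operative event rates, so these are assumptions. With a constant daily hazard h, the proportion seen by day d is 1 − exp(−h·d).
- Assumed 10% by day 21: h = −ln(0.9)/21 = 0.0050 per day. Proportion seen: 3.5% by day 7, 4.9% by day 10, 6.8% by day 14, 10% by day 21.
- Infection, assumed 10% by day 14: h = −ln(0.9)/14 = 0.0075 per day. Proportion seen if counting stops at discharge on day 7, 8 or 10: 5.1%, 5.8% or 7.2%.

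**4. What a difference in stay does to the arm comparison.** Assumptions: the same risk in both arms; stay lognormal with log-scale SD 0.5; window W = stay, raised to 7 days if shorter and cut to 21 if longer. The captured proportion is the average of 1 − exp(−H(W)), where H is the cumulative hazard, found by simulation.
- *Constant hazard:* H(t) = h·t with h = 1% or 2% per day.
- *Early-peaking hazard:* the hazard halves every L days, so H(t) = c·(1 − 2^(−t/L)), with c set so that 25.9% have an event by day 30. This matches the constant 1% case: 1 − exp(−0.30) = 25.9%.

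| Hazard | Captured, median stay 10 d | 12 d | 14 d | Excess, 12 vs 10 d | Excess, 14 vs 10 d | Captured at 10 d as share of day-30 total |
|---|---|---|---|---|---|---|
| 1% per day | 10.6% | 12.0% | 13.3% | 13% | 25% | 41% |
| 2% per day | 20.0% | 22.4% | 24.6% | 12% | 23% | 44% |
| Halving every 7 d | 18.4% | 19.5% | 20.5% | 6% | 12% | 71% |
| Halving every 3 d | 23.5% | 24.0% | 24.5% | 2% | 4% | 91% |

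The excess is the relative increase in patients with a captured event. Across these assumptions it runs from about 2% to about 25%.

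**5. A limit of this model.** With a 10-day median, the share of stays under 7 days is Φ(ln(0.7)/0.5) = Φ(−0.71) = 24%. The model treats these patients as observed to day 7, although the plan gives them no in-window Visit 2.

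**The case against.** The strongest objection is that Section 11.2.1 does not say Visit 2. The final study visit is undefined, patients remain on study for a year, and Section 9.1.6 speaks of capture throughout. A reader could infer that SAEs after discharge are certainly lost; the documents do not establish that. Death, renal replacement therapy and renal dysfunction are followed to one year whatever the discharge date. What remains is that Visit 2 is the last thing called a visit. If a one-year window was meant, the text leaves three sites to choose between windows that differ greatly.

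A reader might also infer that intraoperative events go unrecorded because Visit 1 has no AE step. That is too strong. Sections 9.1.6 and 11.1 require capture throughout and at each visit, and SAEs count from consent. The anesthesiologists are investigators present in the operating room, and Sections 5.3A to 5.3D record coagulopathy, transfusion, vasopressors and blood gases for the operation. The missing entry is an inconsistency in the schedule. Nor is there support for saying that events are lost if a patient dies before Visit 2: death is itself an SAE under Section 11.2. The 10% stopping rule in Section 15.5.2 rests mostly on intraoperative events, which length of stay does not affect. DSMB reviews need occur only every six months, so a delay of one to three weeks would seldom matter.

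Finally, the magnitude depends on assumptions. A constant hazard gives the large figures; a risk concentrated early after surgery, which is plausible for a single intraoperative treatment, gives small ones. This objection stands, so only the range can be reported.

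**Conclusion.** The concern holds for post-operative AEs, SAEs and surgical site infections. On the natural reading of Section 11.2.1, observation ends between day 7 and day 21, can differ threefold between patients and is limited by a secondary endpoint. Patients who leave before day 7 have no compliant closing visit. For surgical site infection the dependence on discharge is explicit in Section 5.3E and conflicts with the synopsis.

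The documents do not allow the size or direction of any bias to be derived. The relative excess of about 2% to 25% rests on assumed median stays of 10 versus 12 to 14 days, equal true risk, a visit held as late as the window allows, and the hazard shapes shown. It is zero if stays do not differ between arms. The primary endpoint is untouched. The missing Visit 1 AE entry and the conflicting day label for Visit 2 are secondary matters of consistency.

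**What to change.** 1. **Section 11.2.1:** replace the reference to the final study visit with one fixed end date after transplant for AEs and SAEs, for example day 30. Apply it to every patient regardless of discharge, and ascertain events from the electronic record already needed for the 30-day endpoints.
2. **Section 5.3E:** count surgical site infections over a fixed two weeks for every patient, in line with the synopsis.
3. **Section 10.1 and Appendix 1:** add an end-of-surgery AE entry so that the schedule matches Sections 9.1.6 and 11.1.
4. **Appendix 1:** reconcile the Day 2 label with the 2 ± 1 week timing. This also settles when patients are asked about throat and swallowing symptoms, for which Section 5.3E gives no day.

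The cost is protocol wording, one CRF page and a small amount of extra chart review at 30 days. Events treated elsewhere may not appear in the record, but the ascertainment period would be the same in both arms.

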12 DISCONTINUATION AND REPLACEMENT OF SUBJECTS

12.1 Early Discontinuation of Study Treatment

A subject may be discontinued from study treatment at any time if the subject, the investigator, or the surgeon feels that it is not in the subject's best interest to continue. The following is a list of possible reasons for study treatment discontinuation:

- Subject withdrawal of consent
- Adverse event that in the opinion of the investigator would be in the best interest of the subject to discontinue study treatment
- Protocol violation requiring discontinuation of study treatment

If a subject is discontinued from treatment due to an adverse event, the subject will be followed and treated by the Investigator until the abnormal parameter or symptom has resolved or stabilized.

Subjects will also be discontinued from the study treatment if the study doctor is unable to place the ECD after three attempts.

12.3 Withdrawal of Subjects from the Study

A subject may be withdrawn from the study at any time if the subject, the investigator, or the Sponsor feels that it is not in the subject's best interest to continue.

All subjects are free to withdraw from participation at any time, for any reason, specified or unspecified, and without prejudice.

Reasonable attempts will be made by the investigator to provide a reason for subject withdrawals. The reason for the subject's withdrawal from the study will be specified in the subject's source documents.

12.4 Replacement of Subjects

Subjects who undergo early discontinuation of the study treatment will not be replaced, and such events will be accounted for by intention-to-treat analysis.

Subjects who withdraw from the study will be replaced with a new subject that will be independently randomized.

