5 CRITERIA FOR EVALUATION

5.1 Primary Efficacy Endpoint

The primary efficacy endpoint is the incidence of AKI within 72 hours after LTx. The International Club for Ascites (ICA) 2015 criteria, a revision of the KDIGO criteria for patients with cirrhosis, will be used to define AKI.³³ The definitions are as follows:

- AKI: increase in sCr \ge 0.3 mg/dL within a 48 hour time window, or a percentage increase \ge 50% from baseline, or initiation of RRT.
- **Baseline sCr**: the most recent value of sCr prior to LTx

A predefined subgroup analysis of the primary outcome will be performed in patients undergoing liver transplantation for hepatocellular carcinoma (HCC) with Model for Endstage Liver Disease exception points.

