8 STUDY TREATMENTS

8.1 Method of Assigning Subjects to Treatment Groups

Up to 230 eligible patients will be randomly assigned to the Experimental Treatment (mild hypothermia) or Control (normothermia) groups in a 1:1 ratio using a block randomization scheme with a randomly chosen block size of 6 or 8 for each block. The randomization scheme was developed by Randomize.net and is accessed through a secure web portal.

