13 PROTOCOL VIOLATIONS

A protocol violation occurs when the subject or investigator fails to adhere to significant protocol requirements affecting the inclusion, exclusion, subject safety and primary endpoint criteria. Protocol violations for this study include, but are not limited to, the following:

- Early termination of temperature management protocol
- Removal of ECD prior to the end of surgery
- Failure to pack the right kidney with ice
- Inability to maintain target temperature for ≥ 1 hour
- Failure to meet inclusion/exclusion criteria
- Failure to comply with Good Clinical Practice (GCP) guidelines will also result in a protocol violation.

Protocol violations will be accounted for by intention-to-treat analysis. Withdrawal of the subject will not be required, as all study procedures are completed within the first visit at the time of LTx.

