15.6 Sample Size and Randomization

Considering one interim analysis for efficacy, and given the incidence of AKI in LTx patients at UCSF (68%), we estimate a sample size of 101 subjects per arm (n = 202 total) is needed to detect a 30% reduction in AKI with 80% power at overall alpha = 0.05 (two-tailed).

We will aim to enroll 230 total subjects to allow for just over a 10% drop-out rate, since some subjects may not be able to complete the protocol and will be withdrawn from the study. UCSF is a high-volume center for LTx (> 180 cases per year), the majority of which meet our inclusion criteria. Thus, we estimate it will take no more than two years to complete study enrollment. The website http://www.swogstat.org was used to perform the power calculation, and the power calculation was confirmed by the CTSI at UCSF.

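### Replacement after study withdrawal (12.4) has no time limit, and ITT (15.3) drops withdrawn patients, so a recorded 72-hour AKI result can be exchanged for a new patient's

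*Combined protocol and SAP*

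**What the plan says.** **Replacement.** Section 12.4 treats two groups differently. For stopping study treatment: "Subjects who undergo early discontinuation of the study treatment will not be replaced, and such events will be accounted for by intention-to-treat analysis". For leaving the study: "Subjects who withdraw from the study will be replaced with a new subject that will be independently randomized". The second rule has no time limit and no condition on the outcome.

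**Who may withdraw a subject, and when.** Section 12.3: "A subject may be withdrawn from the study at any time if the subject, the investigator, or the Sponsor feels" that continuing is not in the subject's interest. The synopsis gives the period: "Subjects will be on study for up to one year". The primary endpoint closes much earlier (5.1): "The primary efficacy endpoint is the incidence of AKI within 72 hours after LTx".

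**Blinding.** Under 8.2 the study anesthesiologists are investigators and are not blinded. The staff who adjudicate AKI are blinded.

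**Analysis set.** Section 15.3 restricts ITT to randomised patients who have not been withdrawn.

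**Numbers.** Section 15.6 needs 202 patients and adds: "We will aim to enroll 230 total subjects to allow for just over a 10% drop-out rate". Its reason is that patients unable to complete the protocol will be withdrawn. Section 8.1 sets a ceiling: "Up to 230 eligible patients will be randomly assigned". Section 15.5.1 counts the interim 101 of 202 net of withdrawals.

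**Protocol violations.** Section 13 lists early termination of temperature management as a violation, handles violations by ITT, and says: "Withdrawal of the subject will not be required, as all study procedures are completed within the first visit".

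**The concern.** The primary outcome is known at 72 hours, but withdrawal with replacement stays open for a year. Under the text as written, a patient withdrawn in month 8 loses a recorded AKI result from the ITT set and a newly randomised patient is added. Some of those entitled to make that decision know the arm and, after 72 hours, can also see the creatinine values. Blinded adjudication protects how each outcome is classified. It does not protect which outcomes are analysed.

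The second problem is that the rules do not fix when enrolment ends or who is in the analysis. Drop-out is provided for in the 230, replacement is promised separately, and randomisation is capped. A patient who cannot complete the temperature protocol is withdrawn under 15.6, but retained under 12.4 and 13.

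**Working it through.** **1. The plan's own sample size.** Inputs from 15.6: control rate 0.68; a 30% relative reduction gives 0.68 × 0.7 = 0.476; power 80%; two-sided alpha 0.05. With mean rate 0.578 and difference d = 0.204:

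- n = [1.960 × √(2 × 0.578 × 0.422) + 0.842 × √(0.68 × 0.32 + 0.476 × 0.524)]² / 0.204² = 90.8
- with continuity correction: (n/4) × [1 + √(1 + 4/(n × d))]² = 100.4, so 101 per arm

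This matches the stated 101 per arm and 202 in total. Using the final-look alpha of 0.0492 also gives 101.

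**2. What 230 already covers.** 230 − 202 = 28 places, and 28/230 = 12.2%. A 10% allowance would need 202/0.9 = 224.4, that is 225. Power without continuity correction at alpha 0.0492 is 0.839 with 101 per arm and 0.883 with 115 per arm. Replacement beyond 230 is not needed for power.

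**3. Where enrolment ends under each reading.**

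| Reading | 5% withdrawn | 10% withdrawn | 15% withdrawn |
|---|---|---|---|
| Replace until 202 non-withdrawn: 202/(1 − w) | 213 | 225 | 238 |
| Replace until 230 non-withdrawn: 230/(1 − w) | 243 | 256 | 271 |
| Stop at 230 randomised | 230 | 230 | 230 |

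The first reading fits under the cap up to 12.2% withdrawal. The second exceeds it at every rate shown. The plan does not say which reading applies.

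**4. What selective withdrawal could do.** These assumptions are not in the documents: no true effect, 68% AKI in both arms, 101 analysed per arm, and k AKI cases withdrawn from the hypothermia arm and replaced by new patients in that arm. The expected hypothermia rate falls by k × 0.32/101.

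| k | Fall in AKI rate | Chance of a false finding favouring hypothermia |
|---|---|---|
| 0 | 0 | 0.024 |
| 5 | 1.6 points | 0.042 |
| 10 | 3.2 points | 0.070 |

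The last column comes from simulation with the two-sample proportion test at 0.0492 two-sided. An exact binomial calculation gives 0.025, 0.043 and 0.070.

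**5. Which sentence causes the bias.** Take k = 5 without replacement: (101 × 0.68 − 5)/96 = 0.663, a fall of 1.7 points. With replacement the fall is 1.6 points. The exclusion in 15.3 produces the bias, and replacement slightly dilutes it. Deleting the replacement sentence alone would therefore leave the problem in place.

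**6. The patient who cannot complete the protocol.** Section 15.6 says withdrawn, which 15.3 turns into exclusion and 12.4 into replacement. Section 12.4 says treatment discontinuations are kept and not replaced. Section 13 says violations are kept and do not require withdrawal. The same patient is in or out of the primary analysis according to the section followed.

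**The case against.** Several points on the other side are sound.

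- **Self-withdrawal only.** Section 12.4 speaks of subjects who withdraw, and 12.3 distinguishes being withdrawn from being free to withdraw. On that reading an investigator or sponsor decision would not trigger replacement. This is possible, but nothing in the text narrows 12.4, and 15.3 excludes withdrawn patients whoever decides. Such decisions must rest on the subject's interest, and the reason for a withdrawal must be recorded. The documents say the study anesthesiologists are unblinded; they do not say so of the sponsor.
- **The cap and replacement can coexist.** The 28 places above 202 can be read as the replacement pool, and the net count in 15.5.1 supports this. It works up to 12.2% withdrawal, so a flat contradiction is not shown. What is missing is the sentence that says so.
- **Late withdrawal does lose data.** There are 90-day and 1-year secondary endpoints. That argues for follow-up where consent allows, not for discarding a recorded primary outcome.
- **Some replacement is legitimate.** A patient who regains capacity and refuses use of data at Visit 2 (10.2) leaves no usable outcome.

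A reader might also infer that replacement fails because the new patient is randomised independently and does not refill the depleted arm. This does not hold. Independent randomisation is sound, since filling a known gap would make allocation predictable. If 12 hypothermia patients of 115 withdrew and were replaced, 109 vs 121 would be expected, with an effective size of 2/(1/109 + 1/121) = 114.7 per arm against 115. That imbalance is not a material harm, and the scenario needs 242 randomised, above the cap. Nor is it right that only remote record review remains after surgery: Visit 2 includes an examination and adverse-event questions.

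**Conclusion.** The concern holds in a limited form. Read together, 12.3, 12.4 and 15.3 allow a recorded 72-hour AKI result to be removed and a new patient's to take its place, at any time in the year. The decision may be made by people who know the arm. The main source of bias is the exclusion in 15.3; the open-ended replacement in 12.4 compounds the problem by leaving the end of enrolment undefined. Separately, 12.4, 13 and 15.6 conflict on patients who cannot complete the protocol.

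The size depends on how many withdrawals are related to outcome, which the documents cannot tell us. Under the stated assumptions, five such cases in one arm bring the one-directional error from about 0.024 to 0.042, and ten to about 0.070. These figures show vulnerability. They are not evidence that anyone would withdraw patients selectively, and withdrawals unrelated to arm and outcome would cause no such bias. The points should be settled before the final analysis.

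**What to change.** 1. **Section 15.3:** define ITT as all randomised patients with a 72-hour outcome whose use is consented to, including those who later withdraw.
2. **Section 12.4:** either delete replacement or limit it to withdrawals that leave no usable 72-hour outcome. In either case, state that no more than 230 are randomised in total.
3. **Section 12.3:** at withdrawal, record whether the subject objects to use of data already collected or only to further follow-up. Separate investigator or sponsor decisions from withdrawal of consent, so that the former do not remove a recorded outcome. The rules on stopping study treatment in 12.1 need not change.
4. **Reconcile 12.3, 12.4, 13, 15.3 and 15.6** on whether a patient who cannot complete the protocol stays in ITT, and say whether the 28 places above 202 are the replacement pool.

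The cost is wording only. The one downside is that there is no top-up if losses exceed 28 of 230 (12.2%). That is modest: with 230 randomised and 15% lost at random, 195.5 patients remain and uncorrected power at alpha 0.0492 is 0.827; with 20% lost, 184 remain and it is 0.803. Fewer would be lost under item 1, because consented outcomes are kept.
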